18.5. VITAL SIGNS

The following Vital Signs measurements will be reported for this study:

Blood Pressure - systolic and diastolic (mmHg)

Respiratory Rate (resp/min)

Pulse Rate (breaths/min)

Temperature (°C)

The actual and change from baseline values for the above parameters will be summarized using descriptive statistics (n, mean, standard deviation, median, and range) by treatment groups and all available visits.

A listing of the above parameters will be provided.

18.6. PHYSICAL EXAMINATION

The physical examination includes evaluation of general appearance, head, eyes, ears, nose, and throat, and the pulmonary, cardiovascular, gastrointestinal, renal/genito-urological, endocrine (including thyroid), musculoskeletal/spinal, lymphatic, and dermatologic systems.

The physical examination will be conducted at screening and EOS.

The frequency and percentage of patients with normal, abnormal CS, and abnormal NCS assessments will be summarized by body system and treatment group at each available visit.

A listings of physical examination findings will be provided.

18.7. OTHER SAFETY ASSESSMENTS (NUMBER OF ASTHMA EXACERBATIONS)

Number of asthma exacerbations will be summarized using frequency count and percentage for the SAF.

Time (in days) from randomization to the first asthma exacerbation will be used as a supportive variable

 $\begin{tabular}{ll} Document: $$ \underline{\abel{localize} Document: ANB020\CYA74392\Biostatistics\Documentation\SAP\Final\20181218} $$ \end{tabular} $$ $$ \underline{\abel{localize} Documentation\SAP\Final\20181218} $$ $$ $\underline{\abel{localize} Documentation\AP\Final\20181218} $$$ $\underline{\abel{localize} Documentation\AP\Final\20181218} $$$ $\underline{\abel{localize} Documentation\AP\Final\20181218} $$$ $\underline{\abel{localize} Docum$

Author: Version Number: 1.0
Version Date: 18Dec2018

Template No: CS_TP_BS016 Revision 4 Reference: CS_WI_BS005

Effective Date: 01Apr2016

Clinical Study Report ANB020-004 - Original

AnaptysBio Inc PROTOCOL ANB020-004 Page 34 of 46

MS Health & Quintiles are now I Q VI A"

STATISTICAL ANALYSIS PLAN

and will be calculated as follows:

Start date of first asthma exacerbation - Date of randomization + 1

The time to first asthma exacerbation for patients who do not experience an asthma exacerbation during the period till end of study will be censored at the date of their last visit, or at the time point after which an exacerbation could not be assessed (for lost to follow-up patients).

Time to first asthma exacerbation will be analyzed to explore the extent to which treatment delays the time to first exacerbation compared with placebo. A cox proportional hazard model will be deployed by using treatment group as a class variable and number of exacerbations in the study as covariates. Results of the analysis will be summarized as hazard ratios and 95% confidence intervals (CIs) comparing ANB020 with placebo.

Time to first asthma exacerbation will be displayed graphically using a Kaplan-Meier plot.

The median time to event will be summarized by treatment groups, if there is sufficient uncensored data available to calculate these median values.

18.8. OTHER SAFETY ASSESSMENTS (IMMUNOGENICITY)

Blood samples will be taken for ADA analysis at day 1, 8, 36, 85, 106, and 127/ET.

Titer values will be summarized by treatment using appropriate descriptive statistics. The frequency and percentage of patients with categorical result assessments will be summarized by treatment groups at each available visit and time points.

19. PHARMACOKINETIC OUTCOMES

The PK parameters will be derived using non-compartmental methods. The actual elapsed sampling times will be used in the PK parameter calculations, except any interim analysis will use nominal sampling times.

The PK analysis set will be used for PK analysis.

Patient listings of PK sampling dates and times and all concentration-time data for each treatment will be presented.

Concentration data of ANB020 will be summarized by treatment and nominal time point, as described in Section 6. Concentrations below the lower limit of quantitation

Document: \\ieedc-vnasc01\biosdata\AnaptysBio\ANB020\CYA74392\Biostatistics\Documentation\SAP\Final\20181218 \\
Author: \text{Version Number: 1.0}

Version Date: 18Dec2018

Template No: CS_TP_BS016 Revision 4 Reference: CS_WI_BS005

Effective Date: 01Apr2016

Clinical Study Report ANB020-004 - Original

AnaptysBio Inc PROTOCOL ANB020-004 Page 35 of 46

(BLQ) will be treated as zero for calculation of descriptive statistics. If the calculated mean concentration is BLQ, the mean value will be reported as BLQ and the SD and CV will be reported as not determined (ND). Missing data will not be inputted, except any missing pre-dose concentrations will be assigned a value of zero for calculation PK parameters. If 1 or more concentrations at a given time point are missing, they will be reported as missing and will be omitted from the calculation of descriptive statistics.

Plots of the mean (±SD) plasma concentration-time profile for ANB020 will be presented by nominal sampling time on linear and semi-logarithmic scales. Individual concentration-time data will be listed and plotted by actual sampling times on linear and semi-logarithmic scales.

For the calculation of PK parameters, concentrations that are BLQ will be assigned a value of zero if they precede quantifiable samples prior to t_{max}. Any anomalous concentration values observed at predose will be identified in the study report and will be used for the computation of PK parameters if the anomalous value is not greater than 5% of C_{max}. If the anomalous value is greater than 5% of C_{max}, the PK parameters for the given patient will be included in listings but excluded from summary presentations and analyses. Following C_{max}, BLQ values embedded between 2 quantifiable data points will be treated as missing. Trailing BLQ values (BLQ values after the last quantifiable concentration) will be set to zero. If consecutive BLQ concentrations are followed by quantifiable concentrations in the terminal portion of the concentration curve, these quantified values will be excluded from the PK analysis by setting them to missina.

The following PK parameters will be computed for ANB020, if data permits:

C_{max}	Maximum concentration in serum (µg/mL), obtained directly from the
	observed concentration versus time data.
t_{max}	Time of maximum concentration (h), obtained directly from the observed
	concentration versus time data.
$\mathrm{AUC}_{(0\text{-inf})}$	Area under the concentration-time curve in serum from time zero (pre-dose)
	extrapolated to infinite time (h·µg/mL), calculated by linear up/log down
	trapezoidal summation and extrapolated to infinity by addition of the last
	quantifiable concentration divided by the apparent terminal rate constant:
	$AUC_{(0-last)} + C_{last}/\lambda_z$.

\\ieedc-vnasc01\biosdata\AnaptysBio\ANB020\CYA74392\Biostatistics\Documentation\SAP\Final\20181218 Document: Author: Version Number:

> Version Date: 18Dec2018

Reference: CS_WI_BS005

Template No: CS_TP_BS016 Revision 4

Effective Date: 01Apr2016

$AUC_{(0\text{-last})}$	Area under the serum concentration-time curve from time zero to the time of
	the last quantifiable concentration (h· μ g/mL), calculated by linear up/log
	down trapezoidal summation.
CL	Systemic clearance (L/h), calculated as dose/ AUC _{0-inf} .
λ_{z}	Apparent terminal rate constant (1/h), determined by linear regression of the
	terminal points of the log-linear concentration-time curve.
$t_{1/2}$	Apparent terminal half-life (h), determined as (ln2/ λ_z).
Vz	Volume of distribution (L) during terminal phase, estimated by dividing the
	systemic clearance by λ_z .
V_{SS}	Volume of distribution at steady state following intravenous dosing (L),
	$calculated \ as \ [([AUMC_{last} + ([t_{last}*C_{last}]/\lambda z) + C_{last}/\lambda z^2]/\ AUC_{(0\text{-inf})}) - TI/(2\pi i \pi i$
	2]*CL, where AUMC _{last} is the area under the moment curve from the time of
	dosing to C_{last} , t_{last} is the time of C_{la} st, and TI is infusion duration.

The following ANB020 PK parameters will be calculated for diagnostic purposes and listed, but will not be summarized:

A 1		TD1 4 4 4 1	/1 \	C /1 '	1 0	1 1 1 1	1'	. 1
	lower	I he start time	· /h	l of the in	terval of	the log-	linear regressioi	n to determine λ_z
/ \v/Z	OWCI	The start time	(11)	or une m	ici vai oi	uic iog-i	illicai iegiessioi	1 to determine /vz

and $t_{1/2}$.

 λ_z upper The end time (h) of the interval of the log-linear regression to determine λ_z

and $t_{1/2}$.

 $t_{1/2}$, Interval The time interval (h) of the log-linear regression to determine λ_z and $t_{1/2}$,

calculated as λ_z upper $-\lambda_z$ lower.

 $t_{1/2}$, N Number of data points included in the log-linear regression analysis used to

calculate λ_z and $t_{1/2}$. A minimum of 3 data points is required.

 R_{sq} Coefficient of determination for calculation of λ_z . A minimum of 3 data

points (excluding C_{max}) will be used for determination of the terminal linear

Document: \\ieedc-vnasc01\\biosdata\AnaptysBio\ANB020\CYA74392\\Biostatistics\Documentation\SAP\Final\20181218\\
Author: \text{Version Number: 1.0}

thor: Version Number: 1.0
Version Date: 18Dec2018

Template No: CS_TP_BS016 Revision 4 Reference: CS_WI_BS005

Effective Date: 01Apr2016

AnaptysBio Inc PROTOCOL ANB020-004 Page 37 of 46

phase of the concentration-time profile. If the Rsq is less than 0.800 then λ_z , $t_{1/2}$, $AUC_{(0\text{-inf})}$, CL, V_Z , and V_{SS} will be listed but not included in summary presentations or analyses.

%AUC_{ex}

Percentage of AUC_(0-inf) obtained by extrapolation, calculated as [(C_{last}/ λ_z)/ AUC_(0-inf)×100]. If the extrapolated area is greater than 20.0% of AUC_(0-inf), then AUC_(0-inf), CL, V_Z, and V_{SS} will be listed but not included in summary presentations or analyses.

The PK parameters will be summarized by treatment as described in Section 6.

PHARMACODYNAMIC OUTCOMES

20. The PD analysis set will be used for PD analysis. The PD endpoints are:

Eosinophil count

Cytokines: IL-4, IL-5, IL-13, IL-33, and sST2

Ex-vivo induced IFN- y

Observed, change from baseline, and ratio to baseline for all PD endpoints will be summarized by treatment and nominal time point using descriptive statistics as described in Section 6. Values that are BLQ will be treated as ½ LLOQ for calculation of descriptive statistics and change from baseline. If the calculated mean is BLQ, the mean value will be reported as BLQ and the SD and CV will be reported as not determined (ND). Missing data will not be imputed. If 1 or more values at a given time point are missing, they will be reported as missing and will be omitted from the calculation of descriptive statistics and change from baseline. If the pre-dose value is missing for baseline, the screening value, if available, will be used as the baseline.

For comparison of the primary PD endpoint between the two treatments, change from baseline in peripheral eosinophil count for each post-dose time point will be analyzed by an MMRM analysis with fixed terms for treatment, time point of measurement, and treatment by time point interaction, baseline eosinophil count as a covariate, and a repeated time point effect within a subject. An unstructured covariance matrix will be used with subject as the experimental unit. If the model fails to converge, then

Document: \\ieedc-vnasc01\biosdata\AnaptysBio\ANB020\CYA74392\Biostatistics\Documentation\SAP\Final\20181218 \\
Author: \text{Version Number: 1.0}

Version Number: 1.0

Version Date: 18Dec2018

Template No: CS_TP_BS016 Revision 4 Reference: CS_WI_BS005

Effective Date: 01Apr2016

AnaptysBio, ANB020 CONFIDENTIAL

IND 126765, SN 0035

Clinical Study Report ANB020-004 - Original

AnaptysBio Inc PROTOCOL ANB020-004 Page 38 of 46

IQVIA STATISTICAL ANALYSIS PLAN

appropriate covariance matrix (e.g., compound symmetric) will be selected based on AIC. The same model will be used to compare the overall average between the treatment groups. All tests of treatment effects will be conducted at a 2-sided alpha level of 0.05 or with 2-sided 95% CIs. The following statistics will be presented:

Treatment LSM

SE of LS Mean

95% CI for LS mean

Treatment LSM difference

SE of LS Mean Difference

95% CI for LSM treatment difference

P-value for comparison of ANB020 versus placebo

For secondary and exploratory endpoints (ex vivo induced IFN-y and serum cytokines), comparison between ANB020 and placebo will be performed using a similar MMRM analysis as described above for primary PD endpoint.

Ratio to baseline values may be used where change from baseline analysis does not meet analysis assumptions. Suitable transformations (e.g., log) may be applied upon such parameters as appropriate to meet the analysis assumptions.

Plots of the mean (±95% CI) observed and change from baseline versus time profiles for PD endpoints will be presented by nominal sampling time on a linear scale.

Plots of observed PD endpoints versus ANB020 concentration will be presented for coinciding nominal time points.

A listing of PD blood sample collection date and times will be provided.

21. Interim/Intermediate Analysis

No interim analysis is planned for the study. However, there will be two unblinded intermediate analysis will be performed once all patients complete the day 36 assessments and again once all patients complete the day 64 assessments. The following 2 data cuts will be provided for data review to unblinded statistician.

Document: \\ieedc-vnasc01\biosdata\AnaptysBio\ANB020\CYA74392\Biostatistics\Documentation\SAP\Final\20181218 Author: Version Number:

> Version Date: 18Dec2018

Reference: CS_WI_BS005

Template No: CS_TP_BS016 Revision 4

Effective Date: 01Apr2016

39 29 June 2020

AnaptysBio Inc PROTOCOL ANB020-004 Page 39 of 46

D. 36 time point:

STATISTICAL ANALYSIS PLAN

- Safety labs (hematology/chem)
- FEV1
- FeNO
- Safety (AE/SAEs)

D.64 time point:

- Safety labs (hematology/chem)
- FEV1
- FeNO
- Safety (AE/SAEs)
- Demographics (Sex/Age)

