**Table 4.1 Schedule of Events**

Assessment Days	Screening 7-14 days prior to Day1	Day 1	Day 2	Week 1 Day 8	Week 3 Day 22	Week 5 Day 36 (+/-2 days)	Week 7 Day 50 (Phone) (+/-2 days)	Week 8 Day 57 (Phone) (+/-2 days)	Week 9 Day 64 (+/-2 days)	Week 12 Day 85 (+/-2 days)	Week 15 Day 106 (+/-2 days)	Week 18 EOS Day 127/ET g (+/-2 days)
General Assessments												
Informed Consent	X i	X a										
Medical History/Demographics	X											
Inclusion/Exclusion Criteria	X	X e										
Clinical Observations												
Exhaled change in nitric oxide (FeNO)	X	X e	X	X	X	X			X	X	X	X
FEV 1 (Spirometry) j	X	X e	X	X	X	X			X	X	X	X
Patient and study staff completed: Asthma Control Questionnaire j	X	X e		X	X	X			X	X	X	X
Patient Diary k	X	X	X	X	X	X	X	X	X	X	X	X
Investigator's assessment (CGIC) j			X	X	X	X			X	X	X	X
Safety Assessments												
Physical Examination	X											X
Safety Laboratory b	X	X e	X	X	X	X			X	X	X	X
Hematology Panel for Eosinophils c	X	X e	X	X	X	X			X	X	X	X
Vital Signs	X	X	X	X	X	X			X	X	X	X
Urinalysis	X								X	X	X	X
Serum Pregnancy Test (WOCBP Only) b	X		X	X	X	X			X	X	X	X
Urine Pregnancy Test (WOCBP Only)		X e										
FSH d	X											
12-Lead ECG	X											X
Concomitant Medications	X	X	X	X	X	X	X	X	X	X	X	X
Adverse Events h	X	X	X	X	X	X	X	X	X	X	X	X
Virology, TB screening, and Drugs of abuse screen	X b											
Samples for ADA f		X e		X		X				X	X	X

Assessment Days	Screening 7-14 days prior to Day1	Day 1	Day 2	Week 1 Day 8	Week 3 Day 22	Week 5 Day 36 (+/-2 days)	Week 7 Day 50 (Phone) (+/-2 days)	Week 8 Day 57 (Phone) (+/-2 days)	Week 9 Day 64 (+/-2 days)	Week 12 Day 85 (+/-2 days)	Week 15 Day 106 (+/-2 days)	Week 18 EOS Day 127/ET g (+/-2 days)
PK/PD/Biomarker Assessments												
Samples for PK f		X	X	X	X	X			X			
Whole blood sampling for ex vivo induced IFN- $\gamma$ f		X e										X
Serum Sampling for Biomarkers Cytokines f (IL-33, IL-4, IL-5, IL-9, IL-13, sST2)		X e	X	X	X	X			X			X
IP administration												
Administration of ANB020 or Placebo		X										

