## 18.0 APPENDIX VI: PHARMACOKINETIC, INTERFERON-GAMMA, ANTI-DRUG ANTIBODY, AND BIOMARKER CYTOKINES COLLECTION TIME POINTS

Study Visit	Pharmacokinetic Sample Time Point (Serum)	Sample Time Point for ex vivo induced IFN- $\gamma$	Sample Time Point for ADA	Pharmacodynamic Sample Time point for Cytokines (Serum)
Day 1 ANB020/ Placebo Dosing	Pre-dose ( $\geq 5$ minutes)	Pre-dose ( $\geq 5$ minutes)	Pre-dose ( $\geq 5$ minutes)	Pre-dose ( $\geq 5$ minutes)
	0.50 hours ( $\pm 5$ minutes) post-start of infusion			
	EOI ( $\pm 3$ minutes)			
	EOI+3 hours ( $\pm 10$ minutes)			
	EOI+6 hours ( $\pm 10$ minutes)			
Day 2	24 hours ( $\pm 120$ minutes) post-start of infusion			24 hours ( $\pm 120$ minutes) post-start of infusion
Day 8	168 hours ( $\pm 120$ minutes) post-start of infusion		168 hours ( $\pm 120$ minutes) post-start of infusion	168 hours ( $\pm 120$ minutes) post-start of infusion
Day 22	504 hours ( $\pm 120$ minutes) post-start of infusion			504 hours ( $\pm 120$ minutes) post-start of infusion
Day 36	840 hours ( $\pm 120$ minutes) post-start of infusion		840 hours ( $\pm 120$ minutes) post-start of infusion	840 hours ( $\pm 120$ minutes) post-start of infusion
Day 64	1512 hours ( $\pm 120$ minutes) post-start of infusion			1512 hours ( $\pm 120$ minutes) post-start of infusion
Day 85			2016 hours ( $\pm 120$ minutes) post-start of infusion	
Day 106			2520 hours ( $\pm 120$ minutes) post-start of infusion	

Study Visit	Pharmacokinetic Sample Time Point (Serum)	Sample Time Point for ex vivo induced IFN-<math>\gamma</math>	Sample Time Point for ADA	Pharmacodynamic Sample Time point for Cytokines (Serum)
Day 127 EOS/ ET a		3024 hours ( $\pm$ 120 minutes) post-start of infusion	3024 hours ( $\pm$ 120 minutes) post-start of infusion	3024 hours ( $\pm$ 120 minutes) post-start of infusion

Abbreviation: ADA = anti-drug antibody, EOI = actual time of end of infusion, EOS = End of study, ET = early termination, IFN- $\gamma$  = interferon-gamma.

Time point details may shift beginning Day 36 depending on use of +/- 2-day window.

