APPENDIX 2. PROGRAMMING CONVENTIONS FOR OUTPUTS

IQVIA Output Conventions

Outputs will be presented according to the following Global Bios > Processes > GBIOS Processes -

Document: \\ieedc-vnasc01\biosdata\AnaptysBio\ANB020\CYA74392\Biostatistics\Documentation\SAP\Final\20181218 Version Number: 1.0 Author:

Version Date: 18Dec2018

Template No: CS_TP_BS016 Revision 4 Reference: CS_WI_BS005

Effective Date: 01Apr2016

29 June 2020 43

Implementation Guidelines and Templates > General Guidelines and Templates > Output Conventions

Dates & Times

Depending on data available, dates and times will take the form yyyy-mm-ddThh:mm:ss

Spelling Format

English UK

Presentation of Treatment Groups

For outputs, treatment groups will be represented as follows and in that order

Treatment Group	For Tables, Listings and Graphs	Treatment Number
ANB020	Dummy1	1
Placebo	Dummy2	2

Presentation of Visits

For outputs, visits will be represented as follows and in that order:

Long Name (default)	Short Name	Visit Number
Screening (Day 0)	Scr	1
Baseline (Day 1)	BL	2
Day 2	Day002	3
Day 8, week 1	Day008	4
Day 22, week 3	Day022	5
Day 36, week 5	Day036	6
Day 64, week 9	Day064	7
Day 85, week 12	Day085	8
Day 106, week 15	Day106	9
Day 127, week 18 (EOS/ET)	EOS	10

For outputs, visits for PK/PD will be represented as follows and in that order:

Document: \\ieedc-vnasc01\\biosdata\AnaptysBio\ANB020\CYA74392\Biostatistics\Documentation\SAP\Final\20181218

Author:

Version Number: 1.0 Version Date: 18Dec2018

Reference: CS_WI_BS005

Template No: CS_TP_BS016 Revision 4

Effective Date: 01Apr2016

CONFIDENTIAL

STATISTICAL ANALYSIS PLAN

AnaptysBio Inc PROTOCOL ANB020-004 Page 44 of 46

Visit	РК	Ex vivo induced INF-γ	ADA	Cytokines
Day 1	Pre-dose (-0.5 hours) 0.5 hours post SOI EOI EOI+3 hours EOI+6 hours	Pre-dose (-0.5 hours)	Pre-dose (-0.5 hours)	Pre-dose (-0.5 hours)
Day 2	24 hours post SOI	1		24 hours post SOI
Day 8, week 1	168 hours post SOI	168 hours post SOI	168 hours post SOI	168 hours post SOI
Day 22, week 3	504 hours post SOI	1	1	504 hours post SOI
Day 36, week 5	840 hours post SOI	840 hours post SOI	840 hours post SOI	840 hours post SOI
Day 64, week 9	1512 hours post SOI			1512 hours post SOI
Day 85, week 12		2016 hours post SOI	2016 hours post SOI	
Day 106, week	1	2520 hours post SOI	2520 hours post SOI	
Day 127, week 18 (EOS/ET)		3024 hours post SOI	3024 hours post SOI	3024 hours post SOI

Listings

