ells
Page 18 of 19

Figure 14 4 2 6

Mean (±95% CI) Change from Baseline for Ex-vivo IFN-gamma – Pharmacodynamic Analysis Set

A plot similar to Figure 14 4 2 5 will be presented for change from baseline values

Document: \\ieedc-vnasc01\\biosdata\AnaptysBio\ANB020\CYA74392\Biostatistics\Documentation\SAP\Final\20181218 Author:

29 June 2020 160

Version Number:

Version Date:

1.0 18Dec2018

[figure not shown]

Figure Shells

AnaptysBio Inc. PROTOCOL ANB020-004 Page 19 of 19

Figure 14 4 2 7

Scatter Plot of Observed Eosinophil Count versus Serum ANB020 Concentration - Pharmacodynamic Analysis Set

Figure 14 4 2 8

Scatter Plot of Observed Serum Cytokine Levels versus Serum ANB020 Concentration - Pharmacodynamic Analysis Set

Note: All available cytokines will be presented on separate plots

Figure 14 4 2 9

Scatter Plot of Observed Ex-vivo IFN-gamma Levels versus Serum ANB020 Concentration - Pharmacodynamic Analysis Set

Version Date: 18Dec2018

Version Number:

1.0

Document Approval Signature(s)

This document has been signed electronically in compliance with Quintiles electronic signature policies and procedures. This page is a manifestation of the electronic signatures, which may be confirmed within the Quintiles source system in accordance with Quintiles records retention policies.

Note: the Title field in the signature block has been intentionally left blank.

UserName: Title: Date: Thursday, 20 December 2018, 10:54 AM Meaning: I Approve the Document	Eastern Time
UserName: Title: Date: Thursday, 20 December 2018, 11:05 AM Meaning: I Approve the Document	Eastern Time
UserName Title: Date: Thursday, 20 December 2018, 11:34 AM	Eastern Time

Meaning: I Approve the Document

Biostatistics File Note Page 1 of 5

Section A

Customer: AnaptysBio, Inc.

Project Code: CYA74392

Protocol Number: ANB020-004

Title of Note:

Additional analyses outside the scope of final SAP (Version Date:

18DEC2018)

Section B

DESCRIPTION:

Form No.: CS_FM_BS020 Revision 3 Reference: CS_OP_BS001

Effective Date: 12Nov2017

Copyright © 2010, 2012, 2017 IQVIA. All rights reserved. The contents of this document are confidential and proprietary to IQVIA Holdings Inc. and its subsidiaries. Unauthorized use, disclosure or reproduction is strictly prohibited.

CONFIDENTIAL

Biostatistics File Note Page 2 of 5

Background

The note-to-file (NTF) is intended to document the additional analyses that are outside the scope of the final SAP dated 18DEC2018.

Objective

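### Ex vivo IFN-gamma has one scheduled post-dose sample (Day 127/ET) and no scheduled post-dose PK pair, yet the SAP lists five post-dose visits and carries over the eosinophil MMRM, with baseline eosinophils as covariate in the output shell

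*SAP*

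**What the plan says.** **Sampling.** In Protocol Table 4.1 the ex vivo IFN-gamma row is marked on Day 1 (pre-dose) and Day 127/ET only. Protocol Appendix VI agrees: its column "Sample Time Point for ex vivo induced IFN" has a pre-dose entry and one post-dose entry, at 3024 hours. The PK column ends on Day 64, at 1512 hours. Footnote a of that appendix adds that a patient who leaves early gives an IFN-gamma sample at the ET visit, and a PK sample too if that visit falls between Day 1 and Day 64.

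**SAP visit list.** SAP Appendix 2, in the column headed "Ex vivo induced INF", gives Days 8, 36, 85, 106 and 127 after the pre-dose sample.

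**Analysis.** For IFN-gamma and the serum cytokines, SAP Section 20 states that "comparison between ANB020 and placebo will be performed using a similar MMRM analysis as described above for primary PD endpoint". That model has treatment, time point and their interaction, baseline eosinophil count, a repeated time effect with unstructured covariance, and an overall average across visits. The IFN-gamma model output, Table 14.4.2.2.2, is one contrast at Day 127/ET. Its footnote names baseline eosinophil count. Protocol Section 9.7 uses the baseline value of the variable being analysed.

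**PK/PD.** SAP Section 20 also states: "Plots of observed PD endpoints versus ANB020 concentration will be presented for coinciding nominal time points". Figure 14.4.2.9 is titled "Scatter Plot of Observed Ex-vivo IFN-gamma Levels versus Serum ANB020 Concentration".

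**Objective.** The secondary objective is PD activity on ex vivo IFN-gamma, with no time point named (Protocol Section 3.2).

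**The concern.** Three parts of the plan assume repeated IFN-gamma data while the patient is on drug: the visit list in SAP Appendix 2, the MMRM, and the scatter plot against concentration. The supplied protocol collects none of that on schedule. The programmer therefore has a visit list that may not match the data, a model with terms that cannot be estimated, an output footnote naming the wrong covariate, and a figure with nothing informative to plot.

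Interpretation is also at stake. IFN-gamma is the trial's ex vivo test of IL-33 blockade. Its one scheduled post-dose measurement falls 126 days after a single dose, six weeks beyond the 84 days over which Phase I showed inhibition in healthy subjects (Protocol Section 2.1). No difference at Day 127 would be expected if the effect had simply worn off. Reported under a general heading of PD activity, it could be taken as evidence that the drug did not block the target in patients.

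**Working it through.** **1. Nominal times.** Hours = (Day − 1) × 24. Day 127 gives 126 × 24 = 3024 and Day 64 gives 63 × 24 = 1512. Both match Protocol Appendix VI.

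**2. The protocol's half-life figure.** Protocol Section 4.3.4 puts five half-lives at about 70 days. With 14 days, 5 × 14 = 70, which reproduces it. Protocol Section 2.1 reports half-lives of 14 to 17 days (single dose) and 16 to 20 days (multiple dose, IV). Five half-lives at 16, 17 and 20 days would be 80, 85 and 100 days.

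**3. Drug remaining.** Fraction = 0.5^(days since dose / half-life), assuming mono-exponential decline from the dose.

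| Half-life (days) | Day 127 (126 d after dose) | 84 d after dose |
|---|---|---|
| 14 | 0.5^9.00 = 0.20% | 1.56% |
| 16 | 0.5^7.88 = 0.43% | 2.63% |
| 17 | 0.5^7.41 = 0.59% | 3.26% |
| 20 | 0.5^6.30 = 1.27% | 5.44% |

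At Day 22, the primary PD time point (21 days after dosing), the same formula gives 0.5^(21/14) = 35% to 0.5^(21/20) = 48%.

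**4. Visits and PK pairs.** PK days in Protocol Appendix VI are 1, 2, 8, 22, 36 and 64.

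| Source of IFN-gamma schedule | Post-dose IFN-gamma days | Post-dose days shared with PK |
|---|---|---|
| Protocol Table 4.1 and Appendix VI | 127 (one) | none |
| SAP Appendix 2 | 8, 36, 85, 106, 127 (five) | 8 and 36 |

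Days 8, 36, 85 and 106 are in the SAP list but not in the supplied protocol. On the protocol schedule the only shared day is Day 1 pre-dose, before any drug. The only post-dose exception is a patient with an ET visit by Day 64.

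**5. The MMRM with one visit.** The design columns are intercept, treatment, visit, treatment by visit, and baseline. With a single post-dose visit the visit column equals the intercept and the interaction equals treatment, so 5 columns have rank 3. A check on simulated data (24 patients, 12 per arm) gave the same treatment estimate from this model and from an ANCOVA with treatment and baseline (−0.926 in both), with 24 − 3 = 21 residual degrees of freedom. The unstructured covariance falls from 5 × 6 / 2 = 15 parameters on the SAP schedule to 1. The overall average across visits is then simply the Day 127 contrast.

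**The case against.** The strongest objection is that the sparse sampling was chosen. The log for Amendment 2 records that IFN-gamma draws were removed because earlier trials had made them unnecessary. Phase I had shown nearly complete inhibition from 24 hours through 84 days, the last time observed for 300 mg IV, so Day 127 adds information on duration. In an unpowered proof-of-concept study that is a defensible trade-off, and this stands. It explains the protocol schedule, but not a SAP dated 18 December 2018 that still lists five post-dose visits. The Phase I data also come from healthy subjects.

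A reader might also infer more than the documents support:

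- **That the comparison or the secondary objective cannot be delivered.** The ANCOVA equivalent gives exactly the contrast that Table 14.4.2.2.2 asks for, and the objective names no time point.
- **That a null eosinophil result could not be told apart from lack of exposure.** PK is drawn on Day 22, the primary endpoint day, and serum cytokines are paired with PK on Days 2, 8, 22, 36 and 64. Only ex vivo inhibition in patients goes unmeasured while drug levels are high.
- **That so little drug means no inhibition at Day 127.** On the same arithmetic only 1.6% to 5.4% remained at 84 days, when inhibition was still nearly complete. Percent remaining is not percent inhibition.
- **That the SAP shells contradict each other outright.** Table 14.4.2.1.3 prints Baseline and Day 8, and Listing 16.2.9.3 prints Days 1 and 127. Both are example rows with an instruction to extend to all visits.
- **That the SAP departs from its governing protocol.** The SAP cites Amendment 4 (31 October 2018), while the supplied protocol's log ends at Amendment 3 (16 February 2018). The versions do differ: SAP Section 7.2 lists UK and US centres, the protocol UK only. Restored draws cannot be excluded.

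**Conclusion.** The point holds in a limited form. Against the supplied protocol, ex vivo IFN-gamma has one scheduled post-dose sample and no scheduled post-dose PK pair, while SAP Appendix 2 assumes five post-dose visits and two pairs. The Day 127 contrast can be estimated. It speaks to persistence at 18 weeks, not to onset, depth or on-drug inhibition in patients, so a null there says nothing about earlier activity. Figure 14.4.2.9 would have no scheduled post-dose points. The eosinophil covariate in the Table 14.4.2.2.2 footnote conflicts with Protocol Section 9.7 whichever schedule applies.

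The 0.2% to 1.3% range rests on the documents' half-lives of 14 to 20 days and on mono-exponential decline. The visit counts rest on the supplied protocol and would change if Amendment 4 restored draws. The need to reconcile the documents would remain, because the protocol and SAP available to the reader do not agree.

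**What to change.** **Required, text only:**

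1. Check the IFN-gamma schedule in the governing amendment, and align SAP Appendix 2, Table 14.4.2.1.3 and Listing 16.2.9.3 with it.
2. If Day 127 is the only post-dose visit, replace the MMRM for IFN-gamma in SAP Section 20 with an ANCOVA of Day 127 change from baseline, with treatment and baseline IFN-gamma. Label the result duration of effect, and state that a null is not evidence against earlier activity. Since the table is titled Day 127/ET, say also whether an ET sample taken earlier enters this contrast.
3. Correct the Table 14.4.2.2.2 footnote to baseline IFN-gamma. This applies on either schedule.
4. If Day 127 is the only post-dose visit, drop Figure 14.4.2.9.

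The cost is a short SAP and shell revision before unblinding, with no new data.

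**Optional, for the sponsor to weigh:** an on-drug IFN-gamma sample at Day 22 or 36, where blood and PK are already drawn, would give a target-engagement contrast in patients and one scheduled PK pair. The planned blood volume of 295.5 mL is below the 550 mL that Protocol Section 6.2.1 quotes for any 8-week period. It would need a protocol amendment, helps only patients who have not passed those visits, and reopens a decision taken deliberately in Amendment 2, so it is not a required change.
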